- **Enrollment:** After consenting to the study, participants will receive the initial survey via text web-link or email link. **Survey 1** asks questions about the participant's hypertension history, experience with prenatal care and care at delivery, and socio-demographic questions not reliably obtained from the electronic health record. We estimate that this survey will take 15 minutes to complete. Participants will receive a \$10 gift card for completion.
- **Randomization and Procedures before Hospital Discharge:** All participants will receive an Omron [validated blood pressure monitor](#) with appropriately sized cuff (Appendix A) following measurement of their arm circumference. Many of our patients do not obtain blood pressure cuffs postpartum, and they infrequently are covered by insurance providers. Instructions for blood pressure measurements and discharge instructions will be discussed with the patient and sent via MyHealth messaging with the script described in Appendix B. Participants will be instructed to measure blood pressure after being seated for 10 minutes with legs uncrossed and back supported with their arm positioned at the level of their heart. They will be instructed to avoid caffeine and tobacco for 30 minutes prior to measuring blood pressure. If blood pressures reach a predefined target threshold (Interventions C and D), they should wait 15 minutes and repeat the blood pressure measurement. Participants will be instructed to bring their blood pressure cuff to their first follow up appointment for calibration and clinical correlation. At hospital discharge, participants will receive information regarding follow up after HDP: a) seeking care for sustained severe blood pressures ($\geq 160/110$ mmHg at least 15 minutes apart), b) preeclampsia alert symptoms (headache, confusion, or visual changes), and c) scheduling an appointment with a primary care clinician at 3 months postpartum. All patients will receive a written letter explaining the study (Appendix C) that they can take to clinician visits outside the VUMC system. At discharge, a follow up in-person visit for a blood pressure check within 7-10 days postpartum will be requested by the inpatient team, which is our routine practice. Our specific research interventions are:

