Weeks 3-6 after delivery	
 ▶ Check blood pressures once daily ▶ Record BPs daily in MyHealth ▶ Seek urgent care (triage, ED) for sustained severe HTN or symptoms 	
 ▶ Receive BPs notifications weekly ▶ Adjust antihypertensive medications based on sections (C) and (D) below
Communication with obstetric clinicians		
 ▶ Send updates on HTN management at weeks 2, 4, and 6 ▶ Document medication changes in EStar ▶ Send updates to non-VUMC obstetric clinicians with any antihypertensive medication changes
Care Handoffs	
 ▶ Schedule postpartum visit at 4-6 weeks ▶ Schedule a visit with a primary care clinician or cardiologist at month 3 	
 ▶ Ensure that postpartum visits are scheduled by 4-6 weeks ▶ Ensure that primary care or cardiology visits are scheduled at month 3 ▶ Remind patients about all visits

Blood pressure Control

(C) *Standard Blood Pressure Control*: Blood pressure targets will be <150 mmHg systolic and <100 mmHg diastolic consistent with current postpartum recommendations from ACOG. Blood pressure notifications for the HTN program navigator will reflect these parameters and medications will be initiated or titrated to meet these goals. See Appendix J for specifics on management and Appendix L for recommended medication regimens

(D) *Tight Blood Pressure Control*: Blood pressure targets will be <140 mmHg systolic and <90 mmHg diastolic. Blood pressure notifications for the HTN program navigator will reflect these parameters and medications will be initiated or titrated to meet these goals. See Appendix K for specifics on management and Appendix L for recommended medication regimens.

- ▶ **Survey 2** (6-weeks after delivery): Participants will receive the survey via text web-link or email link. Survey 2 asks questions about the participant's experience managing hypertension after delivery, the Mothers On Respect Index (MORI) and the Communication Assessment Tool geared towards postpartum care, the PROMIS Bank v1.0 Anxiety (adaptive) survey, the PROMIS Bank v1.0 Depression (adaptive) survey, the PROMIS Bank v2.0 Instrumental Support (adaptive) survey. We estimate that this survey will take 20 minutes to complete. Participants will receive a \$20 gift card for completion of this survey.

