APPENDIX C: Epic MyHealth Message for Intervention #2 (Tight Control / OB Provider Monitoring)

Dear Ms. [last name],

Thank you for being part of the Vanderbilt Fourth Trimester (V4) study. The V4 study will help us learn how to better care for women with high blood pressure in pregnancy.

You have been assigned to the following interventions:

1. Blood pressure goal: <140/90

From discharge through 6 weeks postpartum, we recommend that your blood pressure be less than 140 mmHg systolic (top number) and less than 90 mmHg diastolic (bottom number). If either the top or the bottom blood pressure is higher than the target, your obstetric provider may consider starting medications or changing your dose of medication.

2. Blood pressure monitoring: Obstetric Provider

- You will be given an appointment to have your blood pressure checked in the office within 10 days of delivery. Usually, you receive a MyHealth message about the appointment.
- For the first 2 weeks after delivery, you should check your blood pressure twice a day
- For weeks 3 to 6, you should check your blood pressure once a day
- If your blood pressures are over the goal above, contact your obstetric provider

3. Preeclampsia Danger Signs

Seek medical attention within an hour if you have any of the following:

- Blood pressure of 160 mmHg systolic (top number) or 110 mmHg diastolic (bottom number) after two blood pressure checks at least 15 minutes or more apart and within 4 hours
- A persistent headache that does not go away with rest, eating, or Tylenol
- Spots in your vision or difficulty seeing
- Difficulty breathing
- Persistent and worsening pain in your belly especially in the mid-upper or right-upper areas

4. Long-term Care

High blood pressure in pregnancy often goes away after delivery, but in some people it stays. Even if it goes away, having high blood pressure in pregnancy can make you higher risk for high blood pressure or heart disease later in life. You should see a primary care provider or cardiologist within 3 months after delivery to discuss ways to improve your heart health and to monitor your blood pressure. Be sure to tell your provider that you had high blood pressure in pregnancy.

Instructions for checking your blood pressure

1. Wait at least 30 minutes after smoking, eating, drinking caffeine (coffee, tea, soda), or exercising.
2. Sit comfortably at a table with both feet on the floor and your arm resting on the table, palm up.

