If you have any questions or concerns about the study, please contact [name] at [contact]

APPENDIX F: Message to Obstetric Providers Intervention #1 (Standard Control / OB Provider Monitoring)

Dear [provider's name and salutation],

Your patient, [patient's name], recently delivered and her pregnancy was complicated by a hypertensive disorder of pregnancy. She is participating in the Vanderbilt Fourth Trimester (V4) Study, which is a randomized controlled trial examining different blood pressure targets and management styles for postpartum hypertension.

Ms. [patient last name] has been assigned to the standard blood pressure control group in line with current recommendations from ACOG. Her target blood pressure is **<150 mmHg systolic and <100 mmHg diastolic**.

As part of the study, your patient will:

- Receive a blood pressure cuff and be taught how to use it properly
- Be scheduled for an in-person blood pressure check within 10 days of delivery
- Be instructed to check blood pressures twice daily for weeks 1-2 after delivery and daily for weeks 3-6
- Contact you if she has blood pressures consistently above this target
- Be advised of preeclampsia danger signs and symptoms
- See you for routine postpartum needs including a postpartum visit
- Be instructed to see a primary care provider or cardiologist within 3 months of delivery

We sincerely appreciate your support for this study. If you have any questions or concerns, please do not hesitate to contact [name] at [contact].

Sincerely,

[name], MS (Primary Investigator)
Maternal-Fetal Medicine

[name] (Co-Primary Investigator)
Maternal-Fetal Medicine Fellow

APPENDIX G: Message to Obstetric Providers **Intervention #2 (Tight Control / OB Provider Monitoring)**

Dear [provider's name and salutation],

Your patient, [patient's name], recently delivered and her pregnancy was complicated by a hypertensive disorder of pregnancy. She is participating in the Vanderbilt Fourth Trimester (V4) Study, which is a randomized controlled trial examining different blood pressure targets and management styles for postpartum hypertension.

Ms. [patient last name] has been assigned to the tight blood pressure control group. Her target blood pressure is **<140 mmHg systolic** and **<90 mmHg diastolic**. We recommend initiating or titrating medications to maintain blood pressures less than 140/90.

As part of the study, your patient will:

- Receive a blood pressure cuff and be taught how to use it properly

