- Be scheduled for an in-person blood pressure check within 10 days of delivery
- Be instructed to check blood pressures twice daily for weeks 1-2 after delivery and daily for weeks 3-6
- Contact you if she has blood pressures consistently above this target
- Be advised of preeclampsia danger signs and symptoms
- See you for routine postpartum needs including a postpartum visit
- Be instructed to see a primary care provider or cardiologist within 3 months of delivery

We sincerely appreciate your support for this study. If you have any questions or concerns, please do not hesitate to contact [name] at [contact].

Sincerely,

[name], MS (Primary Investigator)
Maternal-Fetal Medicine

[name] (Co-Primary Investigator)
Maternal-Fetal Medicine Fellow

APPENDIX H: Message to Obstetric Providers Intervention #3 (Standard Control / Augmented Remote Blood Pressure Monitoring)

Dear [provider's name and salutation],

Your patient, [patient's name], recently delivered and her pregnancy was complicated by a hypertensive disorder of pregnancy. She is participating in the Vanderbilt Fourth Trimester (V4) Study, which is a randomized controlled trial examining different blood pressure targets and management styles for postpartum hypertension.

Ms. [patient last name] has been assigned to the standard blood pressure control group in line with current recommendations from ACOG. Her target blood pressure is **<150 mmHg systolic and <100 mmHg diastolic**.

As part of the study, your patient will:

- Receive a blood pressure cuff and be taught how to use it properly
- Be scheduled for an in-person blood pressure check within 10 days of delivery
- Record blood pressures and send them to the study Hypertension Nurse Manager
- Have all hypertension related issues including blood pressure medications managed by the study Hypertension Nurse Manager in collaboration with Maternal-Fetal Medicine.
- Be advised of preeclampsia danger signs and symptoms
- See you for routine postpartum needs including a postpartum visit
- See a primary care provider or cardiologist within 3 months of delivery

The Hypertension Nurse Manager will send you periodic updates on your patient's hypertension progress.

We sincerely appreciate your support for this study. If you have any questions or concerns, please do not hesitate to contact [name] at [contact].

Sincerely,

[name], MS (Primary Investigator)
Maternal-Fetal Medicine

[name] (Co-Primary Investigator)
Maternal-Fetal Medicine Fellow

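### Under provider monitoring, only the tight-control letter (Appendix G) tells clinicians to treat to goal, so target and prompt cannot be separated; Study Procedures also cites the wrong appendices

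*Combined protocol and SAP*

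**What the plan says.** Table 1 crosses two monitoring approaches with two blood pressure goals, giving groups #1 to #4. Under Blood pressure Control, paragraphs (C) standard and (D) tight each say that "medications will be initiated or titrated to meet these goals".

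The goal reaches the patient's obstetric clinician by letter:

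- Appendix F (#1, standard, provider monitoring) says the patient "has been assigned to the standard blood pressure control group in line with current recommendations from ACOG", gives the target, and tells the clinician that she will "Contact you if she has blood pressures consistently above this target". It says nothing about starting or changing medication.
- Appendix G (#2, tight, provider monitoring) has the same list of what the patient will do, including the contact instruction, and adds "We recommend initiating or titrating medications to maintain blood pressures less than 140/90".
- Appendix H (#3, standard, remote) says the patient will "Have all hypertension related issues including blood pressure medications managed by the study Hypertension Nurse Manager in collaboration with Maternal-Fetal Medicine". Appendix I (#4, tight, remote) says the same. Neither carries a prompt to the provider.

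Study Procedures, in text covering all participants, says discharge instructions are "sent via MyHealth messaging with the script described in Appendix B", and that "All patients will receive a written letter explaining the study (Appendix C) that they can take to clinician visits outside the VUMC system". Appendix B is the MyHealth message for #1, with goal <150/100. The other is headed "APPENDIX C: Epic MyHealth Message for Intervention #2 (Tight Control / OB Provider Monitoring", with goal <140/90. Appendices D and E are the messages for #3 and #4.

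**The concern.** In the remote row the study nurse adjusts medication under either goal, so the provider letter does little to deliver the goal. In the provider row the obstetric clinician prescribes, and the letter is one of the few routes the documents describe by which the assigned goal reaches that clinician. A treat-to-goal sentence in one of the two letters is therefore part of the intervention in #2 and absent from #1.

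The Aim 1 model has two binary factors and their interaction, and it reads the main effects as each intervention alone against standard of care. The tight-control coefficient is then #2 minus #1, the contrast in which the letters differ. The same difference enters the interaction, with the opposite sign.

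The appendix references are a second, separate matter. Followed literally, a standard-control woman would carry to outside clinicians a document stating <140/90, and every woman would hold two conflicting goals.

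**Working it through.** **Texts side by side**

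| Group | Provider letter | Who manages medication | Treat-to-goal sentence to provider |
|---|---|---|---|
| #1 | F | obstetric clinician | no |
| #2 | G | obstetric clinician | yes |
| #3 | H | study nurse | no |
| #4 | I | study nurse | no |

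H and I differ only in the goal group, the target and the remark about ACOG recommendations. The asymmetry lies between F and G alone.

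**Inputs.** SBP SD 17.2, N = 1000, alpha 0.05 and 80% power (Power and Sample Size Considerations; Table 6). Allocation is 1:1:1:1, so 250 per group. Two-sided testing is assumed. The prompt effect d (mmHg) is an assumption; the documents give no value.

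**The plan's own figure.** For 250 v 500 the detectable standardized difference is (1.96 + 0.84) × √(1/250 + 1/500) = 0.217, and power at 0.22 is 0.81. The stated 0.22 reproduces and is not in dispute.

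**Where d falls.** Let m1 to m4 be the group means, and replace m2 by m2 - d:

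- Tight alone, m2 - m1: shifts by -d.
- Tight averaged over monitoring, [(m2 - m1) + (m4 - m3)]/2: shifts by -d/2.
- Interaction, (m4 - m3) - (m2 - m1): shifts by +d.
- Remote monitoring averaged over goals, [(m3 - m1) + (m4 - m2)]/2: shifts by +d/2.

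Aim 1 reads a negative interaction as favouring the combination, so the shift works against the trial's own hypothesis.

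**Scale.** With 250 per group:

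- SE(#2 v #1) = 17.2 × √(2/250) = 1.54 mmHg; 80% power needs 4.3 mmHg.
- SE(interaction) = 17.2 × √(4/250) = 2.18 mmHg; 80% power needs 6.1 mmHg.

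If there is no interaction apart from the prompt, the chance of a significant one is Φ(d/2.18 - 1.96) + Φ(-d/2.18 - 1.96):

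| Assumed d (mmHg) | 0 | 1 | 2 | 3 | 4 |
|---|---|---|---|---|---|
| Chance | 5% | 7% | 15% | 28% | 45% |

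The range is illustrative.

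**Which outcomes are exposed.** In Table 3, mean SBP and DBP are taken at 7-10 days. The office reading comes from the routine check, so any change a clinician makes at that visit follows the reading. Only earlier, patient-initiated contact could let the prompt move it. Severe hypertension and medication use run to 6 weeks and leave time for the prompt to act. They are analysed by logistic regression with the same terms, so the same shifts apply on the log-odds scale, with signs reversed for medication use if the prompt raises it.

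**The appendix references.** Study Procedures names one script (B) and one written letter (C) for everyone. By their titles, B to E are four group-specific MyHealth messages and F to I are provider letters. By title or by the use the body gives them, the rest of A to L are cuff fitting, treatment algorithms and medication regimens. None is a general letter for participants to carry.

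**The case against.** Several points on the other side stand.

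- The sentence in (C) and (D) opens with notifications to the program navigator, who works in the remote groups. It can be read as describing only those groups, in which case Appendix F does not contradict it. The F/G difference remains on either reading.
- The letter may not be the only route. (C) and (D) point to Appendices J, K and L without limiting them to remote monitoring, though the documents do not say whether obstetric providers receive them.
- Appendices B and C both tell the patient that her provider may consider starting or changing medication above target, and F and G share the contact instruction. The gap is one sentence to clinicians.
- The difference may be deliberate. #1 is the control and F describes its target as current ACOG guidance; a letter asking for a departure from usual practice may need to say more. The documents do not state that intention.
- The outcome described as registered, a blood pressure recorded in the office, is not expected to vary by goal.

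Three stronger readings are tempting, and the documents support none of them. A reader might infer that the goal effect is confounded. It is not: allocation is randomised, #2 v #1 validly estimates the packages delivered, and H and I are parallel. A reader might infer that the standard arms are contaminated. Each group has its own titled message, and Appendix C is not a letter explaining the study, so the references are probably outdated; nothing shows that women received the wrong document. A reader might also express d as a share of the plan's 4 mmHg. No d is given, and the 4 mmHg belongs to a 250 v 500 comparison. If the 500 are #2 and #4, only half of them are covered by letter G and the shift there is d/2.

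**Conclusion.** The point holds in limited form. In the provider row, #2 v #1 compares a lower target plus an explicit prompt with a target alone, and the planned analysis cannot separate the two. The size is unknown: -d on the tight-alone coefficient, -d/2 on the averaged tight effect and +d on the interaction. That algebra assumes 0/1 coding and a prompt that acts only in #2. d may be near zero for office SBP and DBP at days 7-10; the 6-week outcomes are more exposed. No power figure in the plan changes.

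The citations of Appendices B and C for all participants do not match what those appendices are, and the general letter cannot be identified among the appendices. That is a documentation error in operative trial materials. Any effect on the goal contrast depends on staff having followed it literally, which the documents do not show.

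**What to change.** 1. Reconcile Appendices F and G with each other and with (C) and (D), or state that the difference is intended and describe the provider-row goal effect as target plus prompt. Which wording to use is for the investigators; this review does not choose it.
2. Correct Study Procedures so that each group is referred to its own message (B, C, D or E).
3. Identify or supply the general study letter, and make sure it does not conflict with the woman's assigned goal.
4. Record which versions of the letters and messages have already been sent, and when.
5. Report the goal effect by monitoring row alongside the averaged effect.

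The cost is a few wording and cross-reference edits with IRB review, a version log, and one added presentation of estimates the Aim 1 model already yields. It needs no new participants or procedures.

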APPENDIX J

STANDARD blood pressure control treatment algorithm:

[figure not shown]
V4 Postpartum Hypertension Management Guidelines **STANDARD CONTROL**

Monitoring Frequency

- Weeks 1-2: daily
- Weeks 3+: weekly

How: Seated for 10 minutes, arm at heart level

- If $>150/100$, wait 15 minutes and recheck
- Record second blood pressure

Antihypertensive Medication Escalation Plan:

Nifedipine XL: 30mg daily, 60mg daily, 90mg daily, 120mg daily
Labetalol: 200mg BID, 400mg BID, 600mg TID, 800mg TID
SBP = Systolic Blood Pressure | DBP = Diastolic Blood Pressure

Alert Symptoms:

Headache, visual changes, difficulty breathing, abdominal pain, sudden weight gain

APPENDIX K

TIGHT blood pressure control treatment algorithm:

[figure not shown]
V4 Postpartum Hypertension Management Guidelines **TIGHT CONTROL**

Monitoring Frequency

- Weeks 1-2: daily
- Weeks 3+: weekly

How: Seated for 10 minutes, arm at heart level

- If $>140/90$, wait 15 minutes and recheck
- Record second blood pressure

Antihypertensive Medication Escalation Plan:

Nifedipine XL: 30mg daily, 60mg daily, 90mg daily, 120mg daily
Labetalol: 200mg BID, 400mg BID, 600mg TID, 800mg TID
SBP = Systolic Blood Pressure | DBP = Diastolic Blood Pressure

Alert Symptoms:

Headache, visual changes, difficulty breathing, abdominal pain, sudden weight gain

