While postpartum patient-reported outcome measures have been developed and validated to study inpatient recovery, lack of consensus exists regarding optimal measures of outpatient recovery.⁹⁵ In a recent systematic review of validated measures used to assess three domains or more of outpatient postpartum recovery, three measures were identified but all had significant limitations.⁹⁶ The authors conclude that assessment may be better achieved using existing methods such as those endorsed by the Patient-Reported Outcomes Measurement Information System initiative (PROMIS).⁹⁶ Therefore, we selected validated PROMIS and NIH Toolbox measures related to depression, anxiety, and social support. Because experience of being listened to or being ignored and dismissed are central drivers of Black women's pregnancy and postpartum experience and health outcomes,^{38,39} we emphasize outcomes related to communication during and satisfaction with clinical encounters such as the Communication Assessment Tool -Team (CAT-T) and the Mothers on Respect index (MORi), a scale developed to assess the nature of respectful patient-provider interactions and their impact on a person's sense of comfort, behavior, and perceptions of racism or discrimination.

VARIABLE NAME	DESCRIPTION	DERIVATION	VALUE
7-10 Day Outcomes			
BPinperson710	BP recorded in person	None	1=yes 0=no
BPMremote710	Any BP recorded remotely	A systolic BP (d710sbp_remote) or a diastolic BP (d710dbp_remote) value is present	1=yes 0=no
BPanyp710	Any BP recorded in person or remotely	If BPinperson710 = 1 or BPMremote710=1	1=yes 0=no
SBP710	SBP value Selected by the following hierarchy: 1) in person SBP, 2) remote SBP - If multiple remote BP values were submitted, selected the SBP from day 8 and average the values.	SBP710 = d710sbp_inperson if d710sbp_inperson is present. If d710sbp_inperson is absent, then use d710sbp_remote.	Continuous
DBP710	DBP value Selected by the following hierarchy: 1) in person DBP, 2) remote DBP - If multiple remote BP	DBP710 = d710dbp_inperson if d710dbp_inperson is present. If	Continuous

	values were submitted, selected the DBP from day 8 and average the values.	d710dbp_inperson is absent, then use d710dbp_remote.	
SBP710_bin	SBP value \geq 140	SBP710 \geq 140	1=yes 0=no
DBP710_bin	DBP value \geq 90	DBP710 \geq 90	1=yes 0=no
ANYhigh_bin	Any BP value \geq 140/90	SBP710 \geq 140 OR DBP710 \geq 90	1=yes 0=no
SBPsevere710_bin	SBP value \geq 160	SBP710 \geq 160	1=yes 0=no

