DBPsevere710_bin	DBP value \geq 110	DBP710 \geq 110	1=yes 0=no
ANYsevere_bin	Any BP value \geq 160/110	SBP710 \geq 160 OR DBP710 \geq 90	1=yes 0=no
dcp_medstart	Any medication started between discharge through week 6 after delivery	n/a	1=yes 0=no
dcpp_medstart	Days postpartum that medication was started	n/a	Continuous
readmit	Hospital readmission	n/a	1=yes 0=no

The two co-primary outcomes are mean systolic blood pressure (SBP) and diastolic blood pressure (DBP) recorded in-office (**Table 3**). In a secondary analysis, we will also include mean blood pressure measurements reported via augmented remote monitoring among women who do not attend in-office visits. The third co-

primary outcome is proportion of participants with sustained severe hypertension during the first 6 weeks postpartum defined as a SBP ≥ 160 or a DBP ≥ 110 on two occasions at least 15 minutes apart.

Secondary Outcomes

We will examine three categories of secondary outcomes (**Table 3**). *Hypertension control and adverse events* includes measures of blood pressure control and events potentially associated with poor blood pressure control such as severe maternal morbidity (SMM) and hospital readmission. Given that our intervention tests different models of care, we will assess *health care utilization* associated with these models including adherence to in-person and remote blood pressure monitoring, medication use, attendance at scheduled visits, and unscheduled visits to an urgent care or emergency room.

Table 3: Study outcomes and time frame for assessment

Hypertension Outcomes		
Blood pressure control (Primary Outcome)	Mean SBP assessed in-office and through all methods	7-10 days
Blood pressure control (Primary Outcome)	Mean DBP assessed in-office and through all methods	7-10 days
Severe hypertension (Primary Outcome)	SBP ≥ 160 or DBP ≥ 110 on two occasions 15 minutes apart and less than 4 hours apart	6 weeks
Hospital readmission	Readmission for hypertension management after delivery discharge	3 weeks
Severe maternal morbidity	Center for Disease Control criteria	6 weeks
Health Care Utilization		
Blood pressure assessment	Proportion who report at least one BP reading post delivery	7-10 days
Medication use	Proportion requiring and/or initiating antihypertensive medications	6 weeks
Urgent care visit	Visit to obstetric triage or an emergency department for hypertension	3 weeks

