- You will be given an appointment to have your blood pressure checked in the office within 10 days from delivery. Usually, you receive a MyHealth message about the appointment.
- For the first 2 weeks after delivery, you should check your blood pressure twice a day. Record your blood pressures every day in the Track My Health feature on your MyHealth app. The Hypertension Nurse Navigator will contact you every weekday to comment on your blood pressures.
- For weeks 3 to 6, you should check your blood pressure once a day unless otherwise instructed. Record your blood pressures every day in the Track My Health feature on your MyHealth app. The Hypertension Nurse Navigator will contact you at least weekly to comment on your blood pressures.
- If your blood pressures are over the goal above, you may be recommended to start medications or change your dose
- The Hypertension Nurse Navigator will update your obstetric provider on your blood pressure management

3. Preeclampsia Danger Signs

Seek medical attention within an hour if you have any of the following:

- Blood pressure of 160 mmHg systolic (top number) or 110 mmHg diastolic (bottom number) after two blood pressure checks at least 15 minutes or more apart and within 4 hours
- A persistent headache that does not go away with rest, eating, or Tylenol
- Spots in your vision or difficulty seeing
- Difficulty breathing
- Persistent and worsening pain in your belly especially in the mid-upper or right-upper areas

4. Long-term Care

High blood pressure in pregnancy often goes away after delivery, but in some people it stays. Even if it goes away, having high blood pressure in pregnancy can make you higher risk for high blood pressure or heart disease later in life. You should see a primary care provider or cardiologist within 3 months after delivery to discuss ways to improve your heart health and to monitor your blood pressure. Be sure to tell your provider that you had high blood pressure in pregnancy

Instructions for checking your blood pressure

1. Wait at least 30 minutes after smoking, eating, drinking caffeine (coffee, tea, soda), or exercising.
2. Sit comfortably at a table with both feet on the floor and your arm resting on the table, palm up.
3. Wrap the cuff around your arm, just above your elbow and not over clothing.
4. Push the button to inflate the cuff and record the blood pressure reading.
5. If the reading is above your goal blood pressure, wait 15 minutes and recheck it

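### In the remote arms, the rule for which home reading is recorded depends on the randomised BP goal, which lowers the recorded rate of ≥140/90 under tight control among women with no office reading

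*Combined protocol and SAP*

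**What the plan says.** Appendix J (standard goal) reads "If $>150/100$, wait 15 minutes and recheck"; Appendix K (tight goal) reads "If $>140/90$, wait 15 minutes and recheck". Both then say "Record second blood pressure". Study Procedures links the repeat to the assigned goal: "If blood pressures reach a predefined target threshold (Interventions C and D), they should wait 15 minutes and repeat the blood pressure measurement". The patient messages do the same ("If the reading is above your goal blood pressure, wait 15 minutes and recheck it") without saying which value to enter.

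The Outcomes derivation table takes SBP710 and DBP710 from the in-person value if there is one, otherwise from the remote value. For several remote values the rule is: "If multiple remote BP values were submitted, selected the SBP from day 8 and average the values". ANYhigh_bin is then "SBP710 \geq 140 OR DBP710 \geq 90"; SBP710_bin and DBP710_bin use the same limits singly. The Outcomes text defines the SBP and DBP co-primaries as in-office means and brings in remote values in a secondary analysis of women who miss the visit. Table 3 labels the primary means more broadly, as covering all methods. Nowhere do the documents require the first reading to be kept, or set one reading rule for the outcome across the two goals.

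**The concern.** The measurement rule depends on a randomised factor. Take a first home reading of 145/88. In arm #3 (standard, remote) it is kept and counts as ≥140/90. In arm #4 (tight, remote) it is repeated and the second value is recorded. Readings selected for being high tend to be lower on repeat, so some of these women drop below the cut-point with no change in their true blood pressure. The effect is concentrated on ≥140/90 because that is both the tight arm's recheck threshold and the outcome limit.

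The Aim 1 model contains both factors and their product. Its tight-goal coefficient is the contrast among provider-monitored women, who are not set up to submit readings through the app, so it is essentially unaffected. The artefact falls mainly on the interaction term, where the plan reads a negative value as a benefit of combining the interventions. A difference in recording could thus be reported as synergy, which is one of the trial's hypotheses.

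**Working it through.** **1. The plan's own yardstick.** Power and Sample Size Considerations claims 80% power for 0.22 SD with 250 v 500 and alpha 0.05 (two-sided assumed). Minimum detectable difference = (1.96 + 0.84) × √(1/250 + 1/500) = 2.80 × 0.0775 = 0.217 SD; power at 0.22 SD is 0.811. The claim reproduces. On SBP, 0.22 × 17.2 = 3.8 mmHg, which the plan rounds to 4. The documents give no figure for ≥140/90 or for the share of women with remote values only.

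**2. Inputs for the null check.**
- From the documents: mean (SD) 138 (17.2) and 83 (11.9); recheck thresholds >150/100 and >140/90; twice-daily readings in weeks 1-2, so two day-8 sessions is the planned case.
- Assumed: within-session ICC 0.5-0.9, SBP-DBP correlation 0.65, readings in whole mmHg, no systematic fall on repeat.

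**3. Method.** 1,000,000 simulated women with no treatment effect. Each reading is the woman's own level plus error, with total SD as in the plan. Error SD = 17.2 × √(1 − ICC), which is 12.2 mmHg at ICC 0.5 and 5.4 mmHg at ICC 0.9. The same women are passed through both recheck rules.

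**4. Results, tight minus standard, among remote-only women.**

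| Quantity | Difference |
|---|---|
| ≥140/90, second value kept, two day-8 sessions averaged | about -5 to -6 points |
| ≥140/90, second value kept, single reading | about -6 to -10 points |
| ≥140/90, both values kept, session means averaged over two sessions | about -3 to -4 points |
| Mean SBP, second value kept | -0.1 to -0.6 mmHg |
| ≥160/110, second value kept, single reading | about +0.6 to +2.7 points |

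A separate run set repeat-error SDs directly, from 4/3 to 10/7 mmHg. For SBP that is an ICC of 1 − 4²/17.2² = 0.95 down to 1 − 10²/17.2² = 0.66. It gave -4.2 to -5.7 points for two averaged sessions and -4.2 to -8.9 for a single reading (at 10/7: 0.499 standard v 0.410 tight). If all day-8 values are pooled with equal weight rather than averaged within session first, keeping both values leaves -1.1 to -1.8 points. If the second reading also falls systematically by an assumed 4/2 mmHg, the two-session difference grows to between -8.8 and -10.1 points.

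**5. Effect on the planned interaction test.** On the linear scale with 250 per cell and p near 0.5, SE = √(4 × 0.25/250) = 0.0632. The shift in SE units is z = share × artefact / 0.0632, and type I error = Φ(−1.96 + z) + Φ(−1.96 − z). For artefacts of 5 and 9 points:

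| Remote-only share (assumed) | z | Type I error |
|---|---|---|
| 20% | 0.16 to 0.28 | 5-6% |
| 40% | 0.32 to 0.57 | 6-9% |
| 60% | 0.47 to 0.85 | 8-14% |

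The lower end of each range is close to the planned two-reading case; the upper end needs single readings. Provider-monitored women who miss the visit contribute no value, so the true SE is somewhat larger and these rates are, on that account, on the high side.

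**6. With one reading rule.** If the first reading is used in both goal arms, P(≥140/90) for a single reading is 0.53 in each and the difference is zero.

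**The case against.** The strongest reply is about scope. The registered outcome is whether an office BP was recorded. The co-primary means in the Outcomes text are in-office. Remote values enter only when no in-person value exists, and ANYhigh_bin is in the derivation table but not in Table 3. All of this stands. A reader might infer that the co-primary means are biased: the in-office means are not touched, and the all-methods means shift by well under 1 mmHg against a planned 4 mmHg.

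The instruction to record the second value may mean recording it as well as the first. It sits in a management guideline whose algorithm figure is not shown, and no message tells participants to discard a reading. That is fair, but keeping both values shrinks the artefact without removing it.

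A reader might also test #3 against #4 directly, which gives a higher error rate (about 7-13% at a 40% share). The plan does not specify that contrast, and the interaction's SE is √2 times as large.

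Two further inferences are not supported. The upward shift in ≥160/110 does not carry over to ANYsevere_bin as written, because its derivation uses DBP ≥90; on that definition the net shift is downward. Nor do the documents show that sustained severe hypertension ("on two occasions at least 15 minutes apart") cannot be confirmed, since they do not name the app as its source.

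**Conclusion.** The concern holds within limits. As written, the recording rule differs by randomised BP goal in arms #3 and #4, and it favours tight control on SBP710_bin, DBP710_bin and ANYhigh_bin for women without an in-person 7-10 day value. The direction was the same under every assumption tried. The size rests on the assumed repeat-reading error, and its effect on inference rests on a remote-only share that the documents do not give. In the planned two-reading case the artefact is about 5 to 6 points among remote-only women, which is a modest inflation of the interaction test unless office attendance is poor. It is no reason to doubt the in-office co-primaries or the tight-goal coefficient. It is a cheap improvement, best made early because first readings that were never recorded cannot be recovered.

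**What to change.** Leave the recheck and the care thresholds unchanged, and separate them from outcome measurement:
- In both remote arms, store the first reading and any repeat, each with its time, flagged so that navigator notifications still follow the care rule.
- State in the derivation table that remote SBP710, DBP710 and their ≥140/90 indicators use the first reading of each session in both goal arms, with the day-8 averaging applied to those first readings.
- Report an in-office-only sensitivity analysis for these indicators.
- Where app data are used for sustained severe hypertension, use the stored first-and-repeat pair.

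The cost is a sentence in Appendices J and K and in the derivation table, one extra app entry after a high first reading, and a separate field or flag so that unconfirmed first readings do not change notifications. The sensitivity analysis needs no new data.
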